### **Study Eligibility Criteria:**

#### **Inclusion Criteria:**

Each participant must meet all of the following criteria to be enrolled in this study:

1. At least 18 years of age at the time of consent (Screening Visit).
2. Investigator assessment that participant understands and is willing and physically able to comply with protocol-mandated follow-up, including all procedures.
3. Participant has provided written informed consent for participation in this study, including all evaluations and procedures as specified in this protocol.
4. Female participants of nonchildbearing potential may be enrolled in the study. Nonchildbearing potential is defined as bilateral tubal ligation > 1 year prior to screening, bilateral oophorectomy, hysterectomy, or menopause. Follicle-stimulating hormone level may be measured at the discretion of the investigator to confirm postmenopausal status.
5. Female participants of childbearing potential may be enrolled in the study if the participant fulfills all the following criteria:
  - Has a negative pregnancy test on the day of vaccination (Day 1).
  - Has practiced adequate contraception or has abstained from all activities that could result in pregnancy for at least 28 days prior to Day 1.
  - Has agreed to continue adequate contraception through 3 months following the last vaccine administration.
  - Is not currently breastfeeding.
  - Adequate female contraception is defined as consistent and correct use of a US Food and Drug Administration–approved contraceptive method in accordance with the product label.
6. Participant must have received their second dose of the mRNA-1273 primary series at least 6 months prior to screening and enrollment (Part A) or have received the mRNA-1273 series and an mRNA-1273 booster dose (50 ug) at least 3 months prior to screening and enrollment (Part B).

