Phase 3 study (mRNA-1273-P301) definition of COVID-19	
The participant must have experienced at least TWO of the following systemic symptoms: Fever (<math>\geq 38^{\circ}\text{C}</math>), chills, myalgia, headache, sore throat, new olfactory and taste disorder(s),
 
OR
 
The participant must have experienced at least ONE of the following respiratory signs/symptoms: cough, shortness of breath or difficulty breathing, OR clinical or radiographical evidence of pneumonia; AND The participant must have at least one NP swab, nasal swab, or saliva sample (or respiratory sample, if hospitalized) positive for SARS-CoV-2 by RT-PCR.

End of Study (EoS)	Completion of the last visit of the last participant in the study or last scheduled procedure, as shown in the schedule of events ( Table 8 ) for the last participant in the study.
Lost to follow-up (LTFU)	A participant who repeatedly fails to return for scheduled visits without stating an intention to withdraw consent and is unable to be contacted by the study site.
MAAE	An AE that leads to an unscheduled visit to a healthcare provider.
Nonchildbearing potential	Surgically sterile (history of bilateral tubal ligation, bilateral oophorectomy, hysterectomy) or postmenopausal (defined as amenorrhea for $\geq 12$ consecutive months prior to screening without an alternative medical cause).
Screen failures	Participants who consent to participate in the clinical study but are not subsequently assigned to treatment.
SAE	
An AE is considered an SAE if, in the view of either the investigator or Sponsor, it results in any of the following outcomes (see Section 7.4.2 for further details of each criterion):
 

• Death

• Is life-threatening

• Inpatient hospitalization or prolongation of existing hospitalization

• Persistent or significant incapacity or substantial disruption of the ability to conduct normal life functions

• Congenital anomaly or birth defect

• Medically important event.

Term/Concept	Definition
Symptomatic COVID-19	The presence of one of the CDC-listed symptoms ( https://www.cdc.gov/coronavirus/2019-ncov/symptoms-testing/symptoms.html ) and a positive RT-PCR test on a respiratory sample.

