##### **4.1. Inclusion Criteria (Part A and Part B)**

Each participant must meet all of the following criteria to be enrolled in this study:

1. At least 18 years of age at the time of consent (Screening Visit).
2. Investigator assessment that participant understands and is willing and physically able to comply with protocol-mandated follow-up, including all procedures.
3. Participant has provided written informed consent for participation in this study, including all evaluations and procedures as specified in this protocol.
4. Female participants of nonchildbearing potential may be enrolled in the study. Nonchildbearing potential is defined as bilateral tubal ligation > 1 year prior to screening, bilateral oophorectomy, hysterectomy, or menopause. Follicle-stimulating hormone (FSH) level may be measured at the discretion of the investigator to confirm postmenopausal status.
5. Female participants of childbearing potential may be enrolled in the study if the participant fulfills all the following criteria:
  - Has a negative pregnancy test on the day of vaccination (Day 1).
  - Has practiced adequate contraception or has abstained from all activities that could result in pregnancy for at least 28 days prior to Day 1.
  - Has agreed to continue adequate contraception through 3 months following the last vaccine administration.
  - Is not currently breastfeeding.
  - Adequate female contraception is defined as consistent and correct use of a US Food and Drug Administration (FDA)-approved contraceptive method in accordance with the product label.

6. Participant must have received their second dose of the mRNA-1273 primary series at least 6 months prior to screening and enrollment (Part A) or have received the mRNA-1273 series and an mRNA-1273 booster dose (50 ug) at least 3 months prior to screening and enrollment (Part B).

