#### **4.2. Exclusion Criteria (Part A and Part B)**

Participants meeting any of the following criteria will be excluded from the study:

1. Had significant exposure to someone with SARS-CoV-2 infection or COVID-19 in the past 14 days, defined by the CDC ([CDCa 2021](#)) as a close contact of someone who has COVID-19.
2. Is acutely ill or febrile (temperature  $\geq 38.0^{\circ}\text{C}/100.4^{\circ}\text{F}$ ) less than 72 hours prior to or at the Screening Visit or Day 1. Participants meeting this criterion may be rescheduled and will retain their initially assigned participant number.
3. Currently has symptomatic acute or unstable chronic disease requiring medical or surgical care, to include significant change in therapy or hospitalization for worsening disease, at the discretion of the investigator.
4. Has a medical, psychiatric, or occupational condition that may pose additional risk as a result of participation, or that could interfere with safety assessments or interpretation of results according to the investigator's judgment.
5. History of myocarditis, pericarditis, or myopericarditis within 2 months prior to Screening. Participants who have not returned to baseline after their convalescent period will also be excluded.
6. Has a current or previous diagnosis of immunocompromising condition to include human immunodeficiency virus, immune-mediated disease requiring immunosuppressive treatment, or other immunosuppressive condition.
7. Has received systemic immunosuppressants or immune-modifying drugs for  $> 14$  days in total within 6 months prior to screening (for corticosteroids  $\geq 10$  mg/day of prednisone equivalent) or is anticipating the need for immunosuppressive treatment at any time during participation in the study.
8. Has received or plans to receive any licensed vaccine  $\leq 28$  days prior to the injection (Day 1) or plans to receive a licensed vaccine within 28 days before or after the study injection, with the exception of influenza vaccines, which may be given 14 days before or after receipt of a study vaccine.
9. Has received systemic immunoglobulins or blood products within 3 months prior to the Screening Visit or plans to receive these during the study.

10. Has donated  $\geq 450$  mL of blood products within 28 days prior to the Screening Visit or plans to donate blood products during the study.

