### **10.3. APPENDIX 3: Contraceptive Guidance**

#### **Definitions: Woman of Childbearing Potential**

Women of childbearing potential are those who are considered fertile following menarche and until becoming postmenopausal unless permanently sterile (see below). If fertility is unclear (eg, amenorrhea in adolescents or athletes) and a menstrual cycle cannot be confirmed before vaccination at Day 1, additional evaluation should be considered.

Women in the following categories are not considered women of childbearing potential:

1. Premenarchal
2. Premenopausal, surgically sterile female with 1 of the following:
  - a. Documented complete hysterectomy
  - b. Documented surgical sterilization

For individuals with permanent infertility due to an alternate medical cause other than the above (eg, Müllerian agenesis, androgen insensitivity), investigator discretion should be applied to determining study entry.

Note: Documentation can come from the site personnel's review of the participant's medical records, medical examination, or medical history interview.

3. Postmenopausal female
  - A postmenopausal state is defined as no menses for 12 months without an alternative medical cause. The following age-specific requirements apply:
    - Women < 50 years of age would be considered postmenopausal if they have been amenorrheic for 12 months or more following cessation of exogenous hormonal treatments and if they have luteinizing hormone and FSH levels in the postmenopausal range for the institution.
    - Women  $\geq 50$  years of age would be considered postmenopausal if they have been amenorrheic for 12 months or more, had radiation-induced menopause with last menses  $> 1$  year ago, had chemotherapy-induced menopause with last menses  $> 1$  year ago.
  - A high FSH level in the postmenopausal range may be used to confirm a postmenopausal state in women not using hormonal replacement therapy (HRT).
  - Females on HRT and whose menopausal status is in doubt will be required to use one of the nonestrogen hormonal highly effective contraception methods if they wish to

continue their HRT during the study. Otherwise, they must discontinue HRT to allow confirmation of postmenopausal status before study enrollment.

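### The breastfeeding bar sits only in inclusion criterion 5, so 4.1 and 4.2 do not exclude a breastfeeding woman classed as nonchildbearing under criterion 4

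*Protocol*

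**What the plan says.** Protocol 4.1 handles female participants in two inclusion criteria. Criterion 4 admits women of nonchildbearing potential and supplies its own definition: "Nonchildbearing potential is defined as bilateral tubal ligation > 1 year prior to screening, bilateral oophorectomy, hysterectomy, or menopause". The synopsis carries the same interval, "bilateral tubal ligation > 1 year prior to screening". Criterion 5 opens "Female participants of childbearing potential may be enrolled in the study if the participant fulfills all the following criteria", and one of the conditions under it is "Is not currently breastfeeding".

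The nearest text in 4.2 is exclusion 4, "Has a medical, psychiatric, or occupational condition that may pose additional risk as a result of participation", which is applied on the investigator's judgment. No exclusion mentions breastfeeding.

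Childbearing status is described in two other places:

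- The glossary defines nonchildbearing potential as "Surgically sterile (history of bilateral tubal ligation, bilateral oophorectomy, hysterectomy) or postmenopausal", the latter meaning amenorrhoea for at least 12 "consecutive months prior to screening without an alternative medical cause". Its separate entry for women of childbearing potential refers the reader to Appendix 3.
- Appendix 3 accepts, for surgically sterile premenopausal women, a documented complete hysterectomy or "Documented surgical sterilization". For menopause it starts from 12 months without menses and no other medical cause, then adds age rules. Under 50, LH and FSH must be in the postmenopausal range. At 50 or over, menopause induced by radiation or chemotherapy is accepted if the last menses were more than 1 year ago.

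Sections 4.1 and 7.3.3 make an FSH test discretionary and do not mention LH.

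**The concern.** Whether a woman can conceive and whether she is feeding an infant are separate questions. Placing the breastfeeding condition under childbearing potential makes the second depend on the first. A woman who cannot become pregnant can still be breastfeeding, and for her the condition disappears.

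The protocol gives no reason for the bar. The natural inference is infant exposure, and sterility in the mother does not alter that. Section 1.3.2 says that the safety profile of mRNA-1283 had not yet been evaluated in clinical studies, and 7.4.6 follows pregnancies and their outcomes but provides no follow-up of a breastfed infant. The stake is participant and infant protection, not inference.

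The differing definitions add a smaller problem. Section 4 allows no waivers of the enrolment criteria, so sites need one clear answer on who falls under criterion 5. A site that consults the glossary or Appendix 3 can classify a woman differently from one that reads only 4.1.

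**Working it through.** There is no figure in the plan to reproduce. The check sets the three texts side by side for each type of woman and asks whether 4.1 and 4.2 bar her if she is breastfeeding. N means nonchildbearing; C means of childbearing potential.

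| Woman | 4.1, criterion 4 | Glossary | Appendix 3 | Barred now by 4.1/4.2 if breastfeeding | After a stand-alone exclusion |
|---|---|---|---|---|---|
| Premenopausal, no surgery | C | C | C | yes | yes |
| Ligation 1 year ago or less | C | N | N | yes | yes |
| Ligation more than 1 year ago | N | N | N | no | yes |
| Bilateral oophorectomy | N | N | not named; N if it counts as surgical sterilisation | no | yes |
| Complete hysterectomy | N | N | N | no | yes |
| Hysterectomy not complete | N | N | hysterectomy item not met | no | yes |

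(The Appendix 3 column assumes that the surgery is documented.)

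**Breastfeeding.** Criterion 4 lists three surgical routes. The bar reaches 0 of 3 now and 3 of 3 after the change. The three rows for ligation more than 1 year ago, oophorectomy and complete hysterectomy show that the gap is inside 4.1 itself. Even if oophorectomy is read as surgical sterilisation in Appendix 3, so that all three texts agree, the gap remains; aligning the definitions would not close it. The routes are not equally likely. A ligation must be more than 1 year old, so a woman ligated at or after her last delivery would be feeding a child older than that. Hysterectomy and oophorectomy carry no interval in criterion 4, so recent surgery counts.

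**Ligation interval.** There are two positions: 4.1 and the synopsis require more than 1 year, while the glossary and Appendix 3 require none. A breastfeeding woman ligated 6 months before screening is of childbearing potential under criterion 4 and so is barred. Under the other two texts she would be classed as nonchildbearing.

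**Surgical list.** Appendix 3 asks for a complete hysterectomy and does not name oophorectomy. Criterion 4 and the glossary name both operations without that qualifier.

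**Menopause.** Two cases separate the texts:

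- Under 50, 12 months of unexplained amenorrhoea, off hormones, no LH or FSH result: N in the glossary, C in Appendix 3, undefined in 4.1. What turns on this is the two contraception conditions of criterion 5 (28 days before Day 1, and 3 months after vaccination). The breastfeeding bar is not at issue under the glossary or Appendix 3, since lactation would be another cause of the amenorrhoea.
- Aged 50 or over, menopause induced by radiation or chemotherapy, last menses more than 1 year ago: N in Appendix 3, but not N in the glossary, because there is another medical cause. Undefined in 4.1.

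**Pregnancy safeguards.** The Day 1 urine test in 7.3.3 and the rule in 7.4.6 against enrolling a woman with a positive screening test are not worded as limited to childbearing potential, so they survive. Neither addresses breastfeeding.

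**The case against.** The strongest reply is that 4.1 sets eligibility. It requires every listed criterion to be met and carries its own ligation definition, and its criteria 4 and 5 are complementary. The glossary and an appendix of contraceptive guidance do not override it, and the glossary's entry on childbearing potential points to Appendix 3. For menopause, Appendix 3 can be read as the glossary's rule plus detail by age, and a discretionary FSH test governs when a test may be done, not who counts as postmenopausal. This largely stands. It reduces the definitional differences to a matter of consistency.

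It also disposes of two stronger readings that a reader might draw. One is that a breastfeeding woman ligated 6 months ago could properly be enrolled; criterion 4 bars her. The other is that SAP 6.2.2 would list her as a violation or not depending on the text a site followed; that listing concerns the inclusion and exclusion criteria, so it follows 4.1.

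The reply does not reach the breastfeeding gap, because that gap arises when 4.1 is read alone. A breastfeeding woman with a hysterectomy satisfies criterion 4, no exclusion names her situation, and she would not appear in the SAP 6.2.2 listing.

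A second reply is that placing the condition under criterion 5 was the sponsor's choice, with exclusion 4 covering the remaining cases. No text says that all breastfeeding women must be barred, so the wider intent is an inference. But exclusion 4 requires a medical, psychiatric or occupational condition and a judgment, so it can exclude some women without being a rule.

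**Conclusion.** The point holds as a minor defect of eligibility wording. As written, 4.1 and 4.2 do not exclude a breastfeeding woman who is nonchildbearing by any of criterion 4's three surgical routes. The ligation interval, the surgical list and the menopause rule also differ between 4.1, the glossary and Appendix 3, with 4.1 governing.

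The size is very small. The study plans up to 420 + 140 = 560 participants of both sexes. The documents give neither the share of women nor rates of breastfeeding or of these operations, so no count can be derived. No endpoint, sample size or analysis changes.

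Three further inferences are not supported. The pregnancy safeguards do not lapse with childbearing status. The recent ligation is not the only case on which the texts differ. And Appendix 3 is not the stricter text throughout: it is stricter on menopause under 50 but looser on treatment-induced menopause at 50 or over.

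The conclusion assumes a literal reading of criteria 4 and 5, and that the sponsor means to keep breastfeeding women out whatever their fertility. If the sponsor meant otherwise, a sentence saying so would settle the matter.

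**What to change.** 1. Add current breastfeeding to 4.2 and the synopsis as a stand-alone exclusion for all participants (number 13), and delete it from criterion 5. This closes the main gap by itself.
2. State that criterion 4 of 4.1 is the operative definition of nonchildbearing potential, and carry its more-than-1-year ligation interval and its surgical list into the glossary and Appendix 3. Dropping Appendix 3's qualifier on hysterectomy leaves eligibility as 4.1 already sets it; a sponsor who wants the qualifier should put it in criterion 4.
3. Optionally, point the word menopause in 4.1, the synopsis and the glossary to Appendix 3, including its existing LH and FSH rule for women under 50. Acknowledge in the amendment that this also adopts Appendix 3's allowance for menopause induced by radiation or chemotherapy at 50 or over, which the glossary's wording would not accept. Some women whom the glossary would place under criterion 5 would then be exempt from the contraception conditions.

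The cost is wording in the next amendment and one added exclusion criterion. With item 3 there is also an LH and FSH test for women under 50 who are to be classed as postmenopausal, which Appendix 3 already requires.

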#### **4.2. Exclusion Criteria (Part A and Part B)**

Participants meeting any of the following criteria will be excluded from the study:

1. Had significant exposure to someone with SARS-CoV-2 infection or COVID-19 in the past 14 days, defined by the CDC ([CDCa 2021](#)) as a close contact of someone who has COVID-19.
2. Is acutely ill or febrile (temperature  $\geq 38.0^{\circ}\text{C}/100.4^{\circ}\text{F}$ ) less than 72 hours prior to or at the Screening Visit or Day 1. Participants meeting this criterion may be rescheduled and will retain their initially assigned participant number.
3. Currently has symptomatic acute or unstable chronic disease requiring medical or surgical care, to include significant change in therapy or hospitalization for worsening disease, at the discretion of the investigator.
4. Has a medical, psychiatric, or occupational condition that may pose additional risk as a result of participation, or that could interfere with safety assessments or interpretation of results according to the investigator's judgment.
5. History of myocarditis, pericarditis, or myopericarditis within 2 months prior to Screening. Participants who have not returned to baseline after their convalescent period will also be excluded.
6. Has a current or previous diagnosis of immunocompromising condition to include human immunodeficiency virus, immune-mediated disease requiring immunosuppressive treatment, or other immunosuppressive condition.
7. Has received systemic immunosuppressants or immune-modifying drugs for  $> 14$  days in total within 6 months prior to screening (for corticosteroids  $\geq 10$  mg/day of prednisone equivalent) or is anticipating the need for immunosuppressive treatment at any time during participation in the study.
8. Has received or plans to receive any licensed vaccine  $\leq 28$  days prior to the injection (Day 1) or plans to receive a licensed vaccine within 28 days before or after the study injection, with the exception of influenza vaccines, which may be given 14 days before or after receipt of a study vaccine.
9. Has received systemic immunoglobulins or blood products within 3 months prior to the Screening Visit or plans to receive these during the study.

10. Has donated  $\geq 450$  mL of blood products within 28 days prior to the Screening Visit or plans to donate blood products during the study.
11. Plans to participate in an interventional clinical trial of an investigational vaccine or drug while participating in this study.
12. Is an immediate family member or household member of study personnel, study site staff, or Sponsor personnel.

#### **4.3. Lifestyle Restrictions**

Participants must not eat or drink anything hot or cold within 10 minutes before oral temperature is taken.

#### **4.4. Screen Failures**

Screen failures are defined as participants who consent to participate in the clinical study but are not subsequently assigned to treatment. A minimum set of screen failure information is required to ensure transparent reporting of screen failures to meet the Consolidated Standards of Reporting Trials publishing requirements and to respond to queries from regulatory authorities. Minimum information includes date of informed consent, demography, reason(s) for screen failure, eligibility criteria, and information on any SAE that may have occurred from the time informed consent was obtained to the time of withdrawal.

